#### *4.1.4 Scheduled Follow-Up Visits*

At each follow-up visit, the following steps should be taken:

- Ensure the evaluations listed in Table 1 are completed.
- A voiding diary completed within seven (7) days prior to the next visit.
- Stimulation should be checked to ensure optimal therapy. If some reduction in symptoms occurred, but the subject no longer feels the stimulation, the stimulation amplitude should be increased. If good results were experienced, but unwanted or uncomfortable stimulation occurs, then stimulation amplitude, pulse width and/or frequency can be adjusted. If the subject did not experience symptom reduction, another electrode configuration should be tried. Refer to Clinician Programmer Manual for more information on ensuring optimal therapy and guidance regarding the stimulator's output limitations.
- A review of the operation of the Remote Control and Charge System use should be given, if

needed.

- Subjects should be reminded to continue to take their medications as prescribed and to be consistent with their fluid intake.

#### *4.1.5 Unscheduled Follow-Up Visits*

Subjects are allowed to make unscheduled follow-up visits as necessary, especially if adjustments to their stimulation are required to improve therapy. At each unscheduled follow-up visit, the following steps should be taken:

- Stimulation should be checked to ensure optimal therapy. If necessary, the clinician or Axonics Representative may adjust the programming parameters to optimize therapy as described in Section 4.1.3.
- A review of the operation of the Remote Control and Charge System use should be given, if needed.
- Subjects should be reminded to continue to take their medications as prescribed and to be consistent with their fluid intake.
- Any new adverse events should be documented.
- If feasible, a 72-hour diary should be completed prior to the visit.

#### *4.1.6 Check-In Visits*

Sites will attempt check-in calls or see the subject in the clinic at approximately 5 months, 10 months, 16 months, and 22 months to ensure subjects are adhering to the protocol and to remind them to complete their 72-hour diaries for the next follow-up visit.

## **4.2 Data Collection**

### *4.2.1 Demographics and Medical History*

General information about the subject population will be collected. The following items will be collected:

- Gender, Race, Age, Education level
- Secondary diagnoses (stress incontinence, urinary frequency, retention, fecal incontinence, other, none)
- Years since diagnosis of UUI
- Number of voids per day, number of leaks per week, and number of nighttime voids from subject recollection
- Past medical and surgical history, including past UUI treatments and medications
- Gravidity and parity of female subjects

### *4.2.2 Vital Signs*

Subject's blood pressure and temperature must be collected. Height and weight will be collected at

baseline.

#### *4.2.3 Procedure Report*

Information pertaining to the implant procedure will be collected, including the following:

- Motor and sensory thresholds (as applicable) obtained on all four electrodes. Thresholds are defined in Section 4.1.2.
- Tined Lead location (S3/S4 sacral foramen, left/right)
- Stylet used (curved or straight)
- Duration of procedure
- Type and amount of antibiotic used

#### *4.2.4 Device Performance Metrics*

The following items will be collected to assess performance of the Axonics SNM System, as applicable:

- Impedances on all electrodes. Impedances should be within 400 to 6000 ohms. Physicians should refer to the Clinician Programmer Manual for information on troubleshooting impedances that are not within range.
- Electrode configurations and stimulation parameters at office arrival and upon departure (after programming optimization)
- Charging history from the Neurostimulator
- Number of hours stimulation has been ON since last visit
- Subject's ability to recharge the device

#### *4.2.5 Voiding Diary*

A voiding diary will be recorded over 72 consecutive hours (3 days) to record the subject's voiding habits. The information collected includes the following:

- Number of voids
- Number of urinary incontinence episodes with magnitude of leakage
- Number of urgency episodes with severity

A member of the study staff must review all 72-hour diary data with the subject before the subject leaves the clinic to ensure that the data was filled out correctly and accurately.

#### *4.2.6 Quality of Life Assessments*

##### *4.2.6.1 EQ-5D*

The EQ-5D is a short, generic, validated quality-of-life instrument used to measure health outcomes. It is widely used to calculate health economic benefits of therapies. It takes about five minutes to complete.

#### *4.2.6.2 ICIQ-OABqol*

The ICIQ-OABqol is a validated quality-of-life questionnaire designed to provide a robust assessment of the impact of OAB in subjects' lives. It consists of 26 questions and takes about 15 minutes to complete.

#### *4.2.7 CCF-FIS*

The Cleveland Clinic Florida Fecal Incontinence Score (CCF-FIS) is a five (5) question survey assessing severity of fecal incontinence symptoms. The questions cover incontinence to gas, liquid, solid, need to wear pad, and lifestyle changes. Each question is scored on a scale from zero (absent) to four (daily). The survey takes less than 5 minutes to complete.

#### *4.2.8 CCCS*

The Cleveland Clinic Constipation Score (CCCS) is an eight (8) question survey that assesses the severity of constipation symptoms. The questions cover the frequency and difficulty of bowel movements, associated sensations of completeness and pain, and the subject assessment of time, assistance, and failure associated with their attempts to evacuate their bowels. The survey takes less than 5 minutes to complete.

#### *4.2.9 Subject Satisfaction with Treatment*

Subjects will be asked to rate how satisfied they are with their treatment. Subjects will also be asked if they were able to successfully charge their device, how easy it is to charge their device, and how they feel about how long and how often they have to charge their device. All responses will be provided on a 7-point Likert scale, ranging either from "Very satisfied" to "Very dissatisfied" or from "Definitely" to "Definitely Not".

#### *4.2.10 Medication Usage*

Subjects will be asked about their medication usage and dosages, including any changes from the previous visit (except at baseline).

#### *4.2.11 Healthcare Utilization*

Subjects will be asked about their healthcare utilization, including visits to medical specialists, hospital stays, and other healthcare use such as physical therapy and acupuncture. This information will be used to assess the reduction in healthcare costs due to SNM therapy.

#### *4.2.12 Screening Tools*

##### *4.2.12.1 PHQ-15*

The Patient Health Questionnaire (PHQ) is a diagnostic tool for mental health disorders used by health care professionals that is quick and easy for patients to complete. The PHQ-15 is used to assess somatic symptom severity and the potential presence of somatization and somatoform disorders.

##### *4.2.12.2 Edmonton Frail Scale*

The Edmonton Frail Scale is an assessment of subject frailty that is administered by a physician or nurse

and takes 20 minutes to assess the 10 frailty domains including general health, cognition, balance, and mobility.

## 5 DATA ANALYSIS AND MANAGEMENT

### 5.1 Data Management Process

Details of the data management process will be specified in the ARTISAN-SNM Data Management Plan.

#### 5.1.1 *Source Documents and Source Document Verification*

Source documentation related to subjects' participation in this study is required. The investigator must maintain original source documents that are accurate, complete, and current. Source documentation includes, but is not limited to the following:

- Subject consent form
- Electronic and paper data collection forms, including subject diaries and questionnaires
- Subject's medical file
- Programmer printouts and/or reports
- Prescribed medications
- Hospitalization/clinical events

Source documentation is also required for all protocol related-testing and in the occurrence of adverse events.

The details of how the subject diaries and questionnaires will be collected will be included in the Data Management Plan. All other data shall be entered into the database directly by the sites using an electronic data capture system (EDC) using electronic Case Report Forms (eCRFs).

The data entry should be done within 7 working days of each study visit, with the exception of Adverse Events. All applicable adverse events must be reported by all possible means to Axonics as described in section 8.7. These means include entering the adverse event data into the study database or e-mailing the information to the dedicated clinical email address.

### 5.2 Data Analysis and Statistical Determination

#### 5.2.1 *Data Analysis*

Axonics, or a designated representative, will be responsible for all data analysis. A detailed statistical analysis plan that details the planned analysis of the data will be created and approved prior to analysis of the endpoints.

Axonics, or a designated representative, will be responsible for compiling and submitting all required reports to governmental agencies.

In support of study conduct, designated Axonics personnel may need to review key data. These personnel will have unrestricted "Read Only" access to the Axonics study database. The DSMB may need to conduct independent verification of the Axonics data analysis and any additional, separate, or independent analysis of data, desired or deemed necessary by the DSMB, will be discussed with Axonics prior to conducting such additional analyses.

Adjustments to the statistical analysis plan and/or protocol will be made as needed and will be documented appropriately with notifications to the competent authorities and IRBs/ECs as required. The primary analysis of the study will be prepared when all subjects reach the primary endpoint and another analysis will be performed at the one-year endpoint. A final report after the study has been completed will also be prepared. The safety related aspects of these analyses and reports will be provided to the DSMB according to the DSMB Charter. The reports will follow ISO 14155: 2011 guidelines. Axonics will be responsible for preparation of the study final report. The report shall be reviewed and signed by all principal investigators and forwarded to IRBs/ECs and FDA/Competent Authorities as required.

### *5.2.2 Sample Size Justification*

The study sample size was initially determined considering that the primary endpoint analysis will be performed in the Trial Responders cohort. The sample size considerations using these assumptions is provided in detail in previous versions of the protocol (Rev A- Rev E).

Based on FDA input, the primary endpoint analysis cohort was changed to all implanted subjects. At this stage (rev F), all subjects have been enrolled and implanted. A justification for why the currently implanted number of subjects is a sufficient sample size is provided below:

The primary effectiveness endpoint hypothesis is that the proportion of all implanted subjects that are Treatment Responders at 6-months is greater than 50% (null proportion).

1. Previous literature on SNM for UUI treatment was used to estimate the expected success rate of all subjects receiving this treatment. These studies have shown approximately 80-85% of the subjects that receive an external trial proceed to a permanent SNM implant. Long-term (>6 month) clinical success is seen in approximately 80-85% of the subjects with permanent implant. Thus, of all subjects that received SNM therapy, approximately 65-70% are therapy responders at long term follow-up.
2. Assuming that the true proportion of Treatment Responders is 65%, one hundred and sixteen (116) implanted subjects at 6-months provides approximately 90% power to show that the percentage of Treatment Responders is greater than 50%, assuming a one-sided Type I error rate of 0.021. The one-sided Type I error rate of 0.021 is used to account for planned early look analyses (per the Statistical analysis plan).
3. Assuming an attrition rate of 20% between enrollment and the implant procedure due to screen failures and withdrawals, the total number of enrolled subjects will be capped at approximately one hundred and forty-five (145). Therefore, the study will continue to enroll subjects until either:
  - One-hundred and forty-five (145) patients are enrolled (“Enrollment Cap”), or

---


 White WM, Mobley JD 3rd, Doggweiler R, Dobmeyer-Dittrich C, Klein FA. Incidence and predictors of complications with sacral neuromodulation. *Urology*. 2009 Apr;73(4):731-5.

- There are at least one hundred and sixteen (116) implanted subjects.

Our primary endpoint analysis will be conducted in **All implanted** subjects.

A secondary endpoint analysis will also be performed in the Trial Responder cohort to be comparable to the published literature and standard clinical practice whereby subjects are only implanted after a successful trial period with an external stimulator.

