#### *5.2.3.1 As-Treated*

The primary endpoint As-Treated analysis will include subjects implanted with the Axonics SNM that have data available. Additionally, implanted subjects with missing data, or subjects that are intraoperative screen failures, will also be included in this analysis, and their data will be imputed based on the circumstance of the missing data. Details on Missing data imputation are provided in Section 11.4.

Adverse event data will be based on all implanted subjects and intra-operative screen failures. Pre-operative screen failures will be excluded from all analyses, and will be presented separately.

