###### Missing not at Random (MNAR):

Subjects that are intraoperative screen failures or explanted or withdrawn due to adverse event(s) or lack of efficacy will be considered treatment failures and their baseline diary data will be used as the primary endpoint diary data.

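### The stated 90% power covers 116 implanted subjects only, while the As-Treated rules add intraoperative screen failures to the primary analysis as non-responders

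*Combined protocol and SAP*

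**What the plan says.** Section 5.2.2, repeated in the synopsis, justifies the sample size after the primary population was changed to all implanted subjects. It states that "one hundred and sixteen (116) implanted subjects at 6-months provides approximately 90% power" for a true rate of 65% against a null of 50%, "assuming a one-sided Type I error rate of 0.021". The 65% is the low end of a literature range, described as: "of all subjects that received SNM therapy, approximately 65-70% are therapy responders at long term follow-up". The only loss allowed for comes before implant: "Assuming an attrition rate of 20% between enrollment and the implant procedure due to screen failures and withdrawals".

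Section 5.2.4.1 plans a one-sided binomial test at 2.1% in all implanted subjects, and 5.2.4.1.1 defines the tested proportion on the same population.

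Section 5.2.3.1, which defines the primary As-Treated analysis, goes further: "implanted subjects with missing data, or subjects that are intraoperative screen failures, will also be included in this analysis". The MNAR rule in 5.2.4.6.1 then scores intraoperative screen failures as treatment failures. It does the same for subjects "explanted or withdrawn due to adverse event(s) or lack of efficacy will be considered treatment failures". Section 3.3.3 says that a subject who fails the intraoperative criteria is not implanted.

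**The concern.** The power statement and the analysis rules describe different denominators. In 5.2.2, screen failures are attrition that happens before the 116 are reached. In 5.2.3.1 and 5.2.4.6.1, the intraoperative ones come back into the primary analysis as certain non-responders. Each one enlarges the denominator and can never be a success, so the number of responders needed among the 116 rises or at best stays the same.

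The passages also disagree on the population itself. Sections 5.2.2, 5.2.4.1 and 5.2.4.1.1 say all implanted subjects, while 5.2.3.1 adds people who were never implanted. Section 5.2.3.2, on the per-protocol set, says screen failures are left out of effectiveness analyses.

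The paragraph is the plan's argument that the number already implanted is sufficient after a late change of primary population. If its power figure belongs to a different analysis, that argument is not yet made.

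**Working it through.** **Inputs from the documents (5.2.2, 5.2.4.1).** N = 116, null 0.50, alternative 0.65 (range 0.65 to 0.70), one-sided alpha 0.021, one-sided binomial test, 20% attrition before implant.

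**Inputs not given, so assumed.** The number k of intraoperative screen failures (0 to 8), and the number m of explants and withdrawals for adverse events or lack of efficacy by month 6 (0 to 6).

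**1. The plan's own figures.**
- Enrolment cap: 116 / 0.80 = 145, which agrees.
- Power by normal approximation with the null variance: z(0.979) = 2.0335; √(0.25/116) = 0.04642; √(0.65 × 0.35/116) = 0.04429. Then (0.15 − 2.0335 × 0.04642) / 0.04429 = 1.255, and Φ(1.255) = 89.5%. This is the stated 90%, for a denominator of exactly 116.

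**2. The exact form of the planned test.** The smallest r with P(Bin(116, 0.5) ≥ r) ≤ 0.021 is r = 70 (actual alpha 0.0161). Power = P(Bin(116, 0.65) ≥ 70) = 87.4%. The gap to 89.5% is exact against approximate method and has nothing to do with attrition.

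**3. Intraoperative failures added as fixed non-responders.** The critical value r comes from Bin(116 + k, 0.5), and the responders can come only from the 116. Power = P(Bin(116, p) ≥ r).

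| k | Denominator | r | Power, p = 0.65 | Power, p = 0.70 |
|---|---|---|---|---|
| 0 | 116 | 70 | 87.4% | 99.0% |
| 1 | 117 | 70 | 87.4% | 99.0% |
| 2 | 118 | 71 | 83.0% | 98.3% |
| 5 | 121 | 73 | 71.6% | 95.9% |
| 8 | 124 | 74 | 64.7% | 93.9% |

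One such subject changes nothing because r stays at 70.

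**4. Failures within the 116 (conditional).** This step applies only if the 65% is a rate among subjects who are not explanted or withdrawn for adverse events or lack of efficacy. Then power = P(Bin(116 − m, 0.65) ≥ 70): 81.7% for m = 2, 74.5% for m = 4 and 65.8% for m = 6, with k = 0. If the 65% already counts these subjects as non-responders, the step does not apply and power stays at 87.4%.

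**5. Losses treated as missing at random.** These are multiply imputed and stay in the denominator. As a rough bound, dropping about 5% or 10% of subjects (n = 110 or 104) leaves exact power at 84.1% or 85.3%. The larger sample has the lower value because of binomial discreteness.

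**The case against.** A reader might infer something stronger: that the 90% requires all 116 subjects to yield 6-month data, and that every explant and every withdrawal for adverse events or lack of efficacy takes power away. The documents do not support that.

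- **The 65% may already contain these failures.** Section 5.2.2 describes it as a rate among everyone who received the therapy, and 5.2.4.1.1 defines the tested proportion over all implanted subjects. On that reading an explant is already a non-responder inside the 65%, and step 4 would count it twice. The documents do not settle the matter.
- **Other missing data stay in the denominator.** Section 5.2.4.6.1 imputes missed visits, deaths and losses to follow-up, so their cost is modest.
- **There is no arithmetic slip.** Both the 90% and the 145 reproduce.
- **The planning rate is the low end of the range.** At 70%, power is 93.9% even with eight intraoperative failures. At 67.5%, five of them give 87.4%.
- **The actual N is not stated.** The plan says at least 116. If 129 were implanted, with no intraoperative failures, exact power at 65% would be 91.2%.

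All of this stands and limits how large the loss can be said to be. It does not answer the point about intraoperative failures. Those subjects receive no therapy, so on the plan's wording they are outside both the 65% and the 116, yet the As-Treated rules count them as failures.

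**Conclusion.** The power statement is wrong as written, because it does not describe the primary analysis that 5.2.3.1 and 5.2.4.6.1 define. For 116 implanted subjects alone, the exact test gives 87.4% where the plan says about 90%. Each intraoperative screen failure after the first can lower that figure: to 83.0% with two, 71.6% with five and 64.7% with eight. This rests on a 65% rate among exactly 116 implanted subjects, complete month-6 data and assumed counts. At 70% the loss is of little consequence.

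A further loss from explants and withdrawals for adverse events or lack of efficacy is conditional on the 65% excluding them, which the documents do not say. The documents therefore do not show that the trial is underpowered. They show that its stated power belongs to a different denominator from the one to be analysed.

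**What to change.** 1. Reconcile 5.2.2, 5.2.3.1, 5.2.4.1, 5.2.4.1.1 and the MNAR rule in 5.2.4.6.1 on whether intraoperative screen failures are in the primary denominator.
2. Restate the power in 5.2.2 and the synopsis by the exact binomial test, using the actual number implanted. If intraoperative failures are included, add their actual number as fixed non-responders. Both counts are settled, since 5.2.2 says implantation is complete.
3. State whether the 65% already counts explants and withdrawals for adverse events or lack of efficacy as non-responders. If it does not, show power over an assumed range of such failures. Do not use accrued counts: the trial is open-label and single-arm, so they would feed observed outcomes into a planning assumption.

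The cost is a recalculation, some aligned wording and possibly a less favourable stated power. No patients are added.

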### *5.2.3. Analysis Sets*

The following analysis sets will be utilized for primary endpoint analyses. All subjects will be included for analysis as defined in the Statistical analysis plan and Study protocol. None of the implanted subjects will be excluded from analysis for reasons such as previous medical history, clinical diagnosis etc.

#### *5.2.3.1 As-Treated*

The primary endpoint As-Treated analysis will include subjects implanted with the Axonics SNM that have data available. Additionally, implanted subjects with missing data, or subjects that are intraoperative screen failures, will also be included in this analysis, and their data will be imputed based on the circumstance of the missing data. Details on Missing data imputation are provided in Section 11.4.

Adverse event data will be based on all implanted subjects and intra-operative screen failures. Pre-operative screen failures will be excluded from all analyses, and will be presented separately.

#### *5.2.3.2 Per Protocol*

The per protocol analysis set will include all subjects in the As-Treated set that have no major protocol deviations (e.g., failed intraoperative testing but was implanted) that would potentially affect study outcomes.

Screen failures will be excluded from effectiveness analyses, and will be presented separately.

All safety data will be summarized and analyzed based on all implanted subjects and intraoperative screen failures.

### *5.2.4 Analysis methods*

#### *5.2.4.1 Primary Endpoint*

The primary effectiveness endpoint is that the proportion of all implanted subjects that are Treatment Responders is greater than 50% at 6-months post-activation. If the proportion of Treatment Responders is statistically greater than 50%, the study will be considered to be a success.

As mentioned above, a secondary endpoint analysis will also be conducted in subjects who are "Trial Responders" to allow for a direct comparison to the published SNM literature where analysis at follow-up visits are performed only in trial responders i.e. subjects that have  $\geq 50\%$  improvement in

symptoms after a one-month trial with an external stimulator.

The primary endpoint will be tested for significance based on a one-sided binomial test (such as Fisher's exact test) at a 2.1% significance level to account for two additional early looks as detailed in the Statistical Analysis Plan.

The primary safety endpoint of the study is the rate of adverse events (AEs) through 6-months.

